5.4.2. Dose Termination

After evaluation of safety, tolerability, and PK data by the SST, Investigator, and if required, any ad hoc members, further dosing at the current level and dose escalation will be terminated if any of the following is observed:

- Three similar SAEs (unless related to disease progression or unrelated to BIIIB105 upon medical review) are reported for participants receiving active study treatment within the same cohort.
- Four or more similar AEs are reported for participants receiving active study treatment (unless related to disease progression or unrelated to BIIIB105 upon

CONFIDENTIAL

The information contained herein may not be used, disclosed, or published without the written consent of Biogen MA Inc.

medical review) that are either not tolerable (as reported by the participant) or deemed a medically unacceptable risk by the SST.

• Sponsor requests that dosing be terminated.

Following the SST review of safety and PK data for Cohort D1 (Part 1), if there is agreement that the current emerging safety, tolerability, and PK data support continued dosing at 120 mg, the abovementioned dose termination rules will no longer apply. The Sponsor may still determine that a dose termination is required at any time due to emerging safety data.

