5.3. Dosing

5.3.1. Dose Escalation (Part 1)

For each dose escalation, safety (AEs/SAEs, vital signs, ECGs, and laboratory parameters) and available PK data will be reviewed. The proposed dose escalation is illustrated in Figure 1 and the proposed dosing groups are as follows:

Participants with ALS:

Cohort A: BIIB105 5 mg (6 participants) or placebo (2 participants)

Cohort B: BIIB105 20 mg (6 participants) or placebo (2 participants)

Cohort C1: BIIB105 60 mg (9 participants) or placebo (3 participants)

Cohort D1: BIIB105 120 mg (approximately 36 participants) or placebo (approximately 12 participants)

Participants with polyQ-ALS:

Cohort C2: BIIB105 60 mg (3 participants) or placebo (1 participant)

Cohort D2: BIIB105 120 mg (approximately 12 participants) or placebo (approximately 6 participants)

See Section 3.1.2 for details regarding the rationale for the starting dose and dose escalation.

After a cohort (Cohorts A, B, C1, and C2) is fully randomized and at least 36 days have elapsed since the randomization and dosing of the eighth participant, a Sponsor SST will hold a dose escalation meeting to review all available blinded safety data from all randomized participants. There must be a minimum of 6 evaluable participants for the dose escalation meeting to occur. In Cohort C2, all 4 participants must be evaluable for the dose escalation meeting to occur. Evaluable participants are defined as those who have completed 3 dosing visits and the Day 36 CV. This CV occurs 1 week after the Day 29 dose, the dose that is projected to result in the targeted steady-state exposures for the cohort. Dosing of Cohort D1 is dependent on the SST approving the safety of Cohort C1, and dosing of Cohort D2 is dependent on an SST approving the safety of Cohort C2.

For Cohort D1, the safety review will occur after the cohort is fully randomized, and at least 92 days have elapsed since the randomization and dosing of the 36th participant. The SST will review all available blinded safety data from all randomized participants in the cohort, which must include a minimum of 33 evaluable participants (those who completed all of the first 5 dosing visits as well as the Day 92 clinic visit). This review will be for a final safety review for Cohort D1. Should Part 1 be terminated early (per Section 5.2.1 and Section 13.4) prior to reaching randomization of the entire D1 cohort or minimal evaluable criteria as defined, a final

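### The three-SAE dose termination rule acts on a dose level but counts within one cohort, so three similar related SAEs split 2+1 across D1 and D2 (or C1 and C2) meet neither numeric trigger

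*Protocol*

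**What the plan says.** Protocol Section 5.4.2 states its consequence by dose: "further dosing at the current level and dose escalation will be terminated if any of the following is observed". Three criteria follow.

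- The first needs three similar SAEs, other than those put down to disease progression or judged unrelated, that "are reported for participants receiving active study treatment within the same cohort".
- The second reads "Four or more similar AEs are reported for participants receiving active study treatment". It has the same exclusions and no cohort limit, but the events must also be intolerable to the participant or judged a medically unacceptable risk.
- The third is a request by the Sponsor.

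If the SST's review of Cohort D1 supports continued 120 mg dosing, "the abovementioned dose termination rules will no longer apply". The section then adds: "The Sponsor may still determine that a dose termination is required at any time due to emerging safety data".

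Section 5.3.1 places two cohorts at each of the upper doses. At 120 mg these are "Cohort D1: BIIB105 120 mg (approximately 36 participants) or placebo (approximately 12 participants") and "Cohort D2: BIIB105 120 mg (approximately 12 participants) or placebo (approximately 6 participants"). At 60 mg they are C1, with 9 active and 3 placebo, and "Cohort C2: BIIB105 60 mg (3 participants) or placebo (1 participant"). Section 5.1.1 allows the two cohorts of each pair to be dosed at the same time.

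Section 5.4.1 works by dose level: one SAE assessed as related suspends dosing at that level and any higher one until the SST has evaluated it.

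**The concern.** The unit of action and the unit of counting differ. Termination applies to a dose, while the SAE count stays inside a cohort, and two cohorts can be on that dose together. The same three events at 120 mg therefore meet the criterion if all fall in D1, and do not if two fall in D1 and one in D2. The less severe AE criterion is not limited to a cohort, so the stricter restriction sits on the more serious events.

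At stake is the point at which continuing a first-in-human dose stops being a matter of judgement. In the split case no numeric limit is reached, and the decision stays with the SST or the Sponsor.

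**Working it through.** **The plan's own figure.** The Version 5 amendment summary explains the present thresholds by the growth of the 120 mg cohorts from 38 to 66 participants. Section 5.3.1 gives (36 + 12) + (12 + 6) = 66. The previous D1 size of 20 plus 18 in D2 gives 38. Both reproduce. The documents give no operating characteristics for the termination rule and no SAE rate.

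**Rule logic, with no rate assumed.** A 2+1 or 1+2 split has at most 2 events in either cohort (below 3) and 3 in total (below 4). Neither count is met. In C2 alone, with 3 active participants and at most one event each, the cohort count needs all three to be affected.

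**Share of sets of three that are split.** Assume equal risk and at most one event per participant. For a and b active participants, share = 1 − [C(a,3) + C(b,3)] / C(a+b,3).

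- 120 mg, 36 + 12: 1 − (7140 + 220)/17296 = 0.574
- 60 mg, 9 + 3: 1 − (84 + 1)/220 = 0.614

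The rules can lapse at the D1 review, which needs D1 fully randomized and 33 evaluable participants but sets no D2 enrolment condition. With only 4 or 6 active D2 participants exposed by then (assumed numbers):

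- 36 + 4: 1 − (7140 + 4)/9880 = 0.277
- 36 + 6: 1 − (7140 + 20)/11480 = 0.376

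**Chance of exactly three SAEs, split.** This is P(Bin(a+b, p) = 3) × share, where p is an assumed SAE rate.

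| Active participants | p = 2% | p = 5% | p = 10% |
|---|---|---|---|
| 120 mg, 36 + 12 | 3.2% | 12.4% | 8.7% |
| 60 mg, 9 + 3 | 0.1% | 1.1% | 5.2% |

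At p = 5% the 120 mg figure is 5.1% with 4 active D2 participants and 7.3% with 6. If the D1 rate is 5% and the D2 rate is 0.5, 2 or 3 times that, with full D2 exposure, it is 7.2%, 17.3% or 17.0%.

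**How often the SAE count is met at 120 mg (36 + 12, equal risk).**

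- By cohort: 1 − P(Bin(36,p) ≤ 2) × P(Bin(12,p) ≤ 2) = 3.6%, 28.2%, 74.4% at 2%, 5%, 10%
- By dose level: P(Bin(48,p) ≥ 3) = 7.1%, 43.3%, 87.1%

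At 5% the difference of 15.1 points is 12.4 points from exactly three, split, plus 2.7 points from 2+2 splits. The 2+2 splits already reach the number four in the second criterion.

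**The case against.** The strongest reply is that cohort counting is deliberate. D1 opens on C1 safety and D2 on C2 safety, the SST may review D1 and D2 separately, and Section 13.5 notes that polyQ-ALS participants may be more sensitive to the drug. Section 5.4.3 refers to dose termination across ongoing cohorts and allows stopping for one subpopulation. Version 5 changed two SAEs to three in this bullet and left the cohort limit alone. So the amendment's reference to the 120 mg total, which it gives together with the 28 participants added to D1, does not prove that a dose-level count was intended. That much stands. It does not close the gap, because Section 5.4.2 as written stops a level: three events in D1 alone already stop 120 mg for D2.

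The second reply is that the split case is covered elsewhere. A reader might infer that three split SAEs would go unreviewed, or that the protocol has no answer to them. The documents do not support that. Each related SAE suspends dosing at that level until the SST evaluates it, and frequency is a named factor in that evaluation. A Sponsor request is itself a termination criterion, and the first criterion also operates only after SST evaluation and medical review. What remains is that carrying on with the cohort is one of seven listed outcomes of the suspension review, so no numeric limit binds.

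Third, practical consequence may be slight. The Part 2 and integrated SAP (Section 2.2) records that 60 mg was raised to 120 mg after an SST review on 13 December 2023. That step required agreement that D1 and D2 data supported it, so the rules had very probably lapsed by then.

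**Conclusion.** The point holds as a minor inconsistency in a safety rule. That a 2+1 split meets neither count follows from the wording alone. The split shares (57% at 120 mg, 61% at 60 mg) rest on equal risk and full planned exposure; the 120 mg share is about 28% to 38% with 4 to 6 active D2 participants.

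It would be tempting to quote 12.4% as the chance that the rule fails. The documents do not support this. The figure needs an assumed 5% SAE rate and all 12 active D2 participants exposed, and it drops to 5% to 7% with 4 to 6. Under its own assumptions it is also an upper bound on neither count being met: the second criterion includes non-serious AEs, so one further similar event could bring the total to four if the events are intolerable or medically unacceptable.

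**What to change.** In the first bullet of Section 5.4.2, replace *within the same cohort* with *within the same cohort or at the same dose level across cohorts*, and keep the threshold of three. Retaining the cohort count means that no existing trigger is lost, including for Cohorts A and B, whose participants move from 5 or 20 mg to 60 mg in Part 2. If separate stopping of polyQ-ALS and other ALS cohorts is intended, Section 5.4.2 should instead say that dose termination applies cohort by cohort.

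The cost is one phrase, matched wherever the Dose Escalation Plan repeats the rule, and no added data. The downside is that the count is met somewhat more often (the 43% against 28% above), and D1 and D2 events together could stop 120 mg for both populations.

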5.4.3. Study Termination

The Sponsor may terminate this study at any time after informing the Investigator, ethics committee, and applicable regulatory agencies. The Sponsor will notify Investigators when the study is to be placed on hold, completed, or terminated.

The study will be terminated if no dose is deemed to be safe.

Other conditions that may warrant termination of the study include, but are not limited to, the following:

- The discovery of an unexpected or serious risk to participants enrolled in the study.
- Dose termination for all ongoing cohorts and no agreement between the SST and Investigator to replace the planned dose of the current or subsequent cohorts with a lower dose.
- A decision on the part of the Sponsor to suspend or discontinue testing, evaluation, or development of the product.

If, in light of emerging data, the Sponsor decides to continue testing, evaluation, or development of the product only for a specific subpopulation of ALS (for example, PolyQ-ALS), the study may be terminated for participants who do not meet criteria for the subpopulation.

5.5. Unscheduled Visits

Data collected during UVs should be recorded on the participant's CRFs only if the data support protocol objectives and/or are required for safety monitoring.

5.6. End of Study

5.6.1. End of Part 1

The end of Part 1 (placebo-controlled study) is last participant, last visit in Part 1. Final analyses of Part 1 will be performed after the last participant, last visit has been completed for Part 1, and the database for Part 1 has been locked.

5.6.2. End of Study

The end of study is last participant, last visit for final collection of data in Study 275AS101.

Following end of study, follow-up on vital status and date of death (if deceased) will be performed for participants who provide optional consent for data collection after study completion.

6. STUDY POPULATION

To be eligible to participate in this study, candidates must meet the following eligibility criteria at Screening or at the timepoint specified in the individual eligibility criterion listed.

For Investigator questions regarding participant eligibility or clinical significance of abnormalities, discussion with the study Medical Monitor is strongly encouraged.

6.1. Inclusion Criteria

6.1.1. Part 1

- 1. Ability of the participant to understand the purpose and risks of the study and indicate informed consent, and the ability of the participant or the participant's legally authorized representative, to provide signed and dated informed consent and authorization to use protected health information in accordance with national and local privacy regulations.
- 2. Aged 18 years or older at the time of informed consent or participant meets the minimum age of consent in accordance with national regulations (whichever is higher).
- 3. All women of childbearing potential and all men must ensure that highly effective contraception is used during the study and for at least and for male participants after their last dose of study treatment. In addition, female participants should not donate eggs for the duration of the study and for at least after their last dose of study treatment, while male participants should not donate sperm for the duration of the study and for at least after their last dose of study treatment.
- 4. Participants in Cohorts A, B, C1, and D1, must meet the laboratory-supported probable, probable, or definite criteria for diagnosing ALS according to the World Federation of Neurology El Escorial criteria (revised according to the Airlie House Conference 1998 [Brooks 2000]). Participants in Cohorts C2 and D2 must meet any of the prior conditions but may also only meet clinically possible criteria for diagnosing ALS, or exhibit weakness attributable to ALS in the presence of ATXN2 intermediate repeats.
- 5. In participants in Cohorts C2 and D2, confirmed intermediate CAG/CAA repeat expansion in the *ATXN2* gene as defined by at least 1 allele carrying 30 to 33 CAG/CAA repeats.
- 6. No known presence or family history of mutations in the SOD1 or FUS genes.
- 7. SVC criteria:
- a. In participants in Cohorts A, B, C1, and D1, $SVC \ge 60\%$ of predicted value as adjusted for sex, age, and height (from the sitting position).
- b. In participants in Cohort C2 and D2, $SVC \ge 50\%$ of predicted value as adjusted for sex, age, and height (from the sitting position).

- 8. If taking riluzole, participant must be on a stable dose for ≥ 30 days prior to Day 1 and expected to remain at that dose until the final study visit, unless the Investigator determines that it should be discontinued for medical reasons, in which case it may not be restarted during the study.
- 9. Participants taking concomitant edaravone at study entry must be on a stable dose for ≥ 60 days prior to the first dose of study treatment (Day 1). Participants taking concomitant edaravone must be willing to continue with the same dose regimen throughout the study, unless the Investigator determines that edaravone should be discontinued for medical reasons, in which case it may not be restarted during the study. Edaravone may not be administered on dosing days of this study.
- 10. Screening values of coagulation parameters including platelet count, INR, PT, and APTT should be within normal ranges. Coagulation tests done at a local laboratory may be used for screening purposes, in order to reduce participant burden. Coagulation tests may be repeated once at the local laboratory if, in the opinion of the Investigator, values of the initial tests are out of range but not clinically significant. Participants with nonclinically significant and stable out-of-range values may be eligible to enroll in the study at the discretion of the Investigator and after a consultation with the Sponsor.
- 11. Has an informant/caregiver who, in the Investigator's judgment, has frequent and sufficient contact with the participant as to be able to provide accurate information about the participant's cognitive and functional abilities at Screening. An informant/caregiver should be available at Screening. The participation of the same informant/caregiver for the duration of the study is encouraged.

6.1.2. Part 2

- 1. Ability of the participant to understand the purpose and risks of the study and indicate informed consent, and the ability of the participant or the participant's legally authorized representative to provide signed and dated informed consent and authorization to use protected health information in accordance with national and local privacy regulations.
- 2. Participants must have completed Study 275AS101 Part 1 through Week 25 (Day 175 Visit for Cohorts A, B, C1, C2; Day 176 Visit for Cohorts D1, D2). This inclusion criterion does not apply to a participant if Part 1 was terminated by the Sponsor before the participant reached Week 25.
- 3. Participants from Cohorts A, B, C1, and C2 must have a washout of ≥16 weeks between the last dose of study treatment received in Study 275AS101 Part 1 and the first dose of BIIB105 received in Study 275AS101 Part 2. Participants from Cohorts D1 and D2 do not require a washout period.
- 4. All women of childbearing potential and all men must ensure that highly effective contraception is used during the study and for at least for female participants and for male participants after their last dose of study treatment. In addition,

female participants should not donate eggs for the duration of the	study and for at least
after their last dose of study treatment, while male partic	ipants should not
donate sperm for the duration of the study and for at least	after their last dose of
study treatment.	_

- 5. If taking riluzole, participant must be on a stable dose for ≥ 30 days prior to Day 1 and expected to remain at that dose until the final study visit, unless the Investigator determines that it should be discontinued for medical reasons, in which case it may not be restarted during the study.
- 6. Participants taking concomitant edaravone at study entry must be on a stable dose for ≥ 60 days prior to the first dose of study treatment (Day 1). Participants taking concomitant edaravone must be willing to continue with the same dose regimen throughout the study, unless the Investigator determines that edaravone should be discontinued for medical reasons, in which case it may not be restarted during the study. Edaravone may not be administered on dosing days of this study.
- 7. Screening values of coagulation parameters including platelet count, INR, PT, and APTT should be within normal ranges. Coagulation tests done at a local laboratory may be used for screening purposes, in order to reduce participant burden. Coagulation tests may be repeated once at the local laboratory if, in the opinion of the Investigator, values of the initial tests are out of range but not clinically significant. Participants with nonclinically significant and stable out-of-range values may be eligible to enroll in the study at the discretion of the Investigator and after a consultation with the Sponsor.

6.2. Exclusion Criteria

6.2.1. Part 1

Medical History and Current Health Status

- 1. History or positive test result at Screening for HIV. The requirement for testing at Screening may be omitted if it is not permitted by local regulations.
- 2. Current hepatitis C infection (defined as positive HCV antibody and detectable HCV RNA). Participants with positive HCV antibody and undetectable *HCV* RNA are eligible to participate in the study.
- 3. Current hepatitis B infection (defined as positive for HbsAg and/or total anti-HBc). Participants with immunity to hepatitis B from previous natural infection (defined as negative HbsAg, positive anti-HBc, and positive anti-HBs) or vaccination (defined as negative HbsAg, negative anti-HBc, and positive anti-HBs) are eligible to participate in the study.
- 4. History of alcohol or substance abuse ≤ 6 months of Screening that would limit participation in the study, as determined by the Investigator.

- 5. Current or anticipated need, in the opinion of the Investigator, of a diaphragm pacing system during the study period.
- 6. Presence of tracheostomy.
- 7. Presence of an untreated or inadequately treated active infection requiring systemic antiviral or antimicrobial therapy at any time during the Screening Period.
- 8. History of a deep venous thrombosis or pulmonary embolism ≤ 2 years of Screening, or since the date of ALS diagnosis, whichever is longer.
- 9. In participants from Cohorts A, B, C1, and D1, history of myocardial infarction, as determined by the Investigator.
- 10. In participants from Cohorts A, B, C1, and D1, poorly controlled type 1 or 2 diabetes mellitus defined as $HbA1c \ge 8\%$ during Screening.
- 11. Ongoing medical condition (e.g., wasting or cachexia, severe anemia) that would, in the opinion of the Investigator, interfere with the conduct or assessments of the study.
- 12. Significant cognitive impairment, clinical dementia, or unstable psychiatric illness, including psychosis, suicidal ideation, suicide attempt, or untreated major depression ≤ 90 days of Screening that in the opinion of the Investigator would interfere with the study procedures.
- 13. History of allergies to anesthetics that will be used for the LP procedure per institutional practice.
- 14. Presence of risk for increased or uncontrolled bleeding and/or risk of bleeding that is not managed optimally and could place a participant at an increased risk for intraoperative or postoperative bleeding. These could include, but are not limited to, anatomical factors at or near the LP site (e.g., vascular abnormalities, neoplasms, or other abnormalities) and underlying disorders of the coagulation cascade, platelet function, or platelet count (e.g., hemophilia, Von Willebrand's disease, liver disease).
- 15. Presence or anticipated need of an implanted shunt for the drainage of CSF or an implanted CNS catheter at any time during the study.
- 16. Presence or anticipated need of an implanted intravenous port/catheter at any time during Part 1 of the study.
- 17. Clinically significant abnormalities in hematology or blood chemistry parameters, as determined by the Investigator that would render the participant unsuitable for enrollment.

- 18. Clinically significant, as determined by the Investigator, 12-lead ECG abnormalities, including corrected QT interval using Fridericia's correction method of > 450 msec for males and > 460 msec for females.
- 19. In participants in Cohorts A, B, and C1, prescreening ALSFRS-R slope > -0.4 points/month, where prescreening ALSFRS-R slope is defined as: (ALSFRS-R score at Screening 48) / (months from date of symptom onset to date of Screening). This criterion is not applicable for Cohorts C2, D1, and D2.

Medications

- 20. Treatment with another investigational drug (including investigational drugs for ALS through compassionate use programs) or biological agent within 1 month or 5 half-lives of study agent, whichever is longer, before Screening.
- 21. Treatment with an approved disease-modifying therapy for ALS other than riluzole or edaravone within 1 month or 5 half-lives of therapy, whichever is longer, before completion of Screening.
- 22. Treatment with an antiplatelet or anticoagulant therapy that cannot safely be interrupted for LP according to local standard of care and/or institutional guidelines, in the opinion of the Investigator or Prescriber.

Other

- 23. Female participants who are pregnant or currently breastfeeding and those intending to become pregnant during the study.
- 24. Current enrollment or a plan to enroll in any interventional clinical study. Participation in a noninterventional study focused on ALS natural history may be allowed at the discretion of the Investigator and after consultation with the Sponsor.
- 25. Inability to comply with study requirements.
- 26. Other unspecified reasons that, in the opinion of the Investigator or the Sponsor, make the participant unsuitable for enrollment.

6.2.2. Part 2

Medical History and Current Health Status

1. History or positive test result at Screening for HIV. The requirement for testing at Screening may be omitted if it is not permitted by local regulations. If participants from Cohorts D1 and D2 who would seamlessly roll from Part 1 into Part 2 test positive for HIV during screening for Part 2 but are clinically asymptomatic, they may enroll in Part 2 at the discretion of the Investigator.

- 2. Current hepatitis C infection (defined as positive HCV antibody and detectable HCV RNA). Participants with positive HCV antibody and undetectable HCV RNA are eligible to participate in the study. If participants from Cohorts D1 and D2 who would seamlessly roll from Part 1 into Part 2 test positive for hepatitis C during screening for Part 2 but are clinically asymptomatic, they may enroll in Part 2 at the discretion of the Investigator.
- 3. Current hepatitis B infection (defined as positive for HbsAg and/or total anti-HBc). Participants with immunity to hepatitis B from previous natural infection (defined as negative HbsAg, positive anti-HBc, and positive anti-HBs) or vaccination (defined as negative HbsAg, negative anti-HBc, and positive anti-HBs) are eligible to participate in the study. If participants from Cohorts D1 and D2 who would seamlessly roll from Part 1 into Part 2 test positive for hepatitis B during screening for Part 2 but are clinically asymptomatic, they may enroll in Part 2 at the discretion of the Investigator.
- 4. History of alcohol or substance abuse ≤ 6 months of Screening that would limit participation in the study, as determined by the Investigator.
- 5. Current or anticipated need, in the opinion of the Investigator, of a diaphragm pacing system during the study period.
- 6. Presence of an untreated or inadequately treated active infection requiring systemic antiviral or antimicrobial therapy at any time during the Screening Period that, according to the Investigator, would interfere with the conduct or assessments of the study.
- 7. In participants from Cohorts A, B, C1, and D1, history of myocardial infarction, as determined by the Investigator.
- 8. In participants from Cohorts A, B, C1, and D1, poorly controlled type 1 or 2 diabetes mellitus defined as $HbA1c \ge 8\%$ during Screening.
- 9. Ongoing medical condition (e.g., wasting or cachexia, severe anemia) that would, in the opinion of the Investigator, interfere with the conduct or assessments of the study.
- 10. Significant cognitive impairment, clinical dementia, or unstable psychiatric illness, including psychosis, suicidal ideation, suicide attempt, or untreated major depression ≤ 90 days of Screening that in the opinion of the Investigator would interfere with the study procedures.
- 11. History of allergies to anesthetics that will be used for the LP procedure per institutional practice.
- 12. Presence of risk for increased or uncontrolled bleeding and/or risk of bleeding that is not managed optimally and could place a participant at an increased risk for intraoperative or postoperative bleeding. These could include, but are not limited to, anatomical factors at or near the LP site (e.g., vascular abnormalities, neoplasms, or other abnormalities) and underlying disorders of the coagulation cascade, platelet function, or platelet count (e.g., hemophilia, Von Willebrand's disease, liver disease).

- 13. Presence or anticipated need of an implanted shunt for the drainage of CSF or an implanted CNS catheter at any time during the study.
- 14. Clinically significant abnormalities in hematology or blood chemistry parameters, as determined by the Investigator that would render the participant unsuitable for enrollment.
- 15. Clinically significant, as determined by the Investigator, 12-lead ECG abnormalities, including corrected QT interval using Fridericia's correction method of > 450 msec for males and > 460 msec for females.

Medications

- 16. Treatment with another investigational drug (including investigational drugs for ALS through compassionate use programs; excluding BIIB105) or biological agent within 1 month or 5 half-lives of study agent, whichever is longer, before Screening.
- 17. Treatment with an antiplatelet or anticoagulant therapy that cannot safely be interrupted for LP according to local standard of care and/or institutional guidelines, in the opinion of the Investigator or Prescriber.

Other

- 18. Female participants who are pregnant or currently breastfeeding and those intending to become pregnant during the study.
- 19. Current enrollment or a plan to enroll in any interventional clinical study. Participation in a noninterventional study focused on ALS natural history may be allowed at the discretion of the Investigator and after consultation with the Sponsor.
- 20. Inability to comply with study requirements.
- 21. Other unspecified reasons that, in the opinion of the Investigator or the Sponsor, make the participant unsuitable for enrollment.

